Concomitant medications allowed: Patients will continue taking previous psychopharmaceutical medications they are using to treat autism. However, we will request, insofar as possible, that no changes take place in the type or doses of their psychopharmaceutical medications for the duration of the study. They will also be allowed to continue taking any other medications, such as anti-epileptic medications for seizure control.

Study visits narrative:

The main study will consist of 2 phases of treatment, each lasting 15 weeks per patient. Phase 1 is the double blind phase, in which 50% of study participants will receive active drug (sulforaphane) and the other 50% will receive active placebo, according to the

dosing schedule as detailed above. In Phase 2, from 15 weeks until 30 weeks is an open-label phase during which all study participants will receive the active drug (sulforaphane). All safety laboratory tests will be performed in a CLIA certified laboratory at the University of Massachusetts Memorial Medical Center. Phase 3 will be from 30 to 36 weeks, without treatment, followed by a final follow up visit at 36 weeks.

The study comprises a total of 6 visits over a period of 36 weeks, with visits spaced around 6-8 weeks apart. In addition there will be two telephone surveys between visit 1 and 2, and between 3 and 4 to detect any possible adverse events. Following is a description of procedures that will be performed at each study visit:

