At this visit, the study participant/s will already have been randomly assigned to either the sulforaphane or placebo group in the ratio of 1:1 by the study statistician. As mentioned above, after the safety labs come back normal, we will mail the study participants (or ask their parents to pick up) an 8 week supply of study medication (sulforaphane or placebo) that will last until the 7 week visit, plus a one week buffer. We will provide detailed instructions to subjects/parents/guardians on how to take the medication and include these instructions along with the medication package, and they will be made aware (and given written instructions) on how to recognize any side effects associated with the medication. They will be asked to call the study staff in case they have any questions or concerns.

2. **7 week visit (double blind Phase 1):** Enrolled subjects will then be asked to come for their 7 week (follow-up) study visit, where OACIS-I, SRS, ABC and Vineland Adaptive Behavior Scale will be administered. A complete physical examination will be performed and vital signs obtained. This visit will take ~ 1.5 hours to complete. They will be asked about any serious side effects they might have experienced. Also, clinical laboratory tests (CBC and platelets, complete metabolic profile (including liver function tests, renal function tests, thyroid function tests) and research laboratory tests blood - (Nrf2, heat shock proteins, measures of oxidative stress and mTOR) and urine (isoprostanes) will be obtained. Maximum amount of blood drawn at any stage during this study will not exceed 2 ml/kg body weight; we will also not exceed the minimal risk limitation of 3 ml/kg in an 8 week period.

At this visit, we will give the study participants a further 7 week supply of study medication (sulforaphane or placebo) that will last until the next visit (15 week visit). Study participants will be asked to finish the medication from the previous lot before starting the latter batch. They will be asked to continue to take the study medication unless instructed otherwise. We will provide detailed instructions for subjects/parents/guardians on how to take the study medication along with the medication package, and they will be made aware (and given written instructions) on how to recognize any side effects associated with the study medication. They will be asked to call the study staff in case they have any questions or concerns.

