If at this visit lab results are found to be abnormal (AST/ALT > 2x upper limit of normal, serum creatinine > 1.2 mg/dl, TSH outside normal limits), we will ask the study participants to discontinue study medication for 2 weeks. After 2 weeks, we will ask them to come for an interim study visit and draw their blood for liver function tests, renal function tests and thyroid function tests. If lab values have returned to within study's acceptable limits (AST/ALT < 2x upper limit of normal, serum creatinine < 1.2 mg/dl, TSH within normal limits), and as advised by the study Data Safety Monitoring Board, we will then ask them to resume the study medication.

After 2 weeks, if the lab tests are still abnormal (AST/ALT > 2x upper limit of normal; serum creatinine > 1.2 mg/dl; TSH outside normal limits), then the study participants will discontinue study medication permanently (though we will ask them continue to be followed-up in the study).

- 4. 22 week visit (open label Phase 2):** Enrolled subjects will then be asked to come for their 22 week (follow-up) study visit, where OACIS-I, SRS, ABC and Vineland Adaptive Behavior Scale will be administered. A complete physical

examination will be performed and vital signs obtained. This visit will take ~ 1.5 hours to complete. They will be asked about any side effects they might have experienced. Also, clinical laboratory tests (CBC and platelets, complete metabolic profile (including liver function tests, renal function tests, thyroid function tests), and research laboratory tests blood- (Nrf2, heat shock proteins, measures of oxidative stress and mTOR) and urine sample for isoprostanes will be obtained. Maximum amount of blood drawn at any stage during this study will not exceed 2 ml/kg body weight; we will also not exceed the minimal risk limitation of 3 ml/kg in an 8 week period.

At this visit, we will give the study participants a further 7 week supply of study medication (sulforaphane) that will last until the next (30 week) visit. We will provide detailed instructions for subjects/parents/guardians on how to take the study medication along with the medication package, and they will be made aware (and given written instructions) on how to recognize any side effects associated with the study medication. They will be asked to call the study staff in case they have any questions or concerns.

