If at this visit lab results are found to be abnormal (AST/ALT > 2x upper limit of normal, serum creatinine > 1.2 mg/dl, TSH outside normal limits), we will ask the study participants to discontinue study medication for 2 weeks. After 2 weeks, we will ask them to come for an interim study visit and draw their blood for liver function tests, renal function tests and thyroid function tests. If lab values have returned to within study's acceptable limits (AST/ALT < 2x upper limit of normal, serum creatinine < 1.2 mg/dl, TSH within normal limits), and as advised by the study Data Safety Monitoring Board, we will then ask them to resume the study medication.

After 2 weeks, if the lab tests are still abnormal (AST/ALT > 2x upper limit of normal; serum creatinine > 1.2 mg/dl; TSH outside normal limits), then the study participants will discontinue study medication permanently (though we will ask them continue to be followed-up in the study).

- 5. 30 week visit (open label Phase 2):** Enrolled subjects will then be asked to come for their 30 week (follow-up) study visit, where OACIS-I, SRS, ABC and Vineland Adaptive Behavior Scale will be administered. A complete physical examination will be performed and vital signs obtained. This visit will take ~ 1.5 hours to complete. They will be asked about any side effects they might have experienced. Also, laboratory tests (CBC and platelets, complete metabolic profile, including liver function tests, renal function tests, thyroid function tests), and research laboratory tests blood - (Nrf2, heat shock proteins, measures of oxidative stress and mTOR) and urine sample for isoprostanes will be obtained. Maximum amount of blood drawn at any stage during this study will not exceed 2 ml/kg body weight; we will also not exceed the minimal risk limitation of 3 ml/kg

in an 8 week period. At this visit, we will not give the study participants any further study medication.

- 6. 36 week final follow-up visit (Phase 3):** This will be the final study visit. OACIS-I, SRS, ABC and Vineland Adaptive Behavior Scale will be administered. A complete physical examination will be performed and vital signs obtained. This visit will take ~ 1.5 hours to complete. Participants and their caregivers will be asked about any side effects they might have experienced. Also, research laboratory tests for blood - (Nrf2, heat shock proteins, measures of oxidative stress and mTOR) and urine sample for isoprostanes will be obtained.

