Following is a description of the telephone surveys:

- 1. Phone survey 1:** This phone call will take place between visits 1 and 2 at approximately 3 weeks from the study drug start date. This will help us ensure that the study participants does not experience any unwanted side effects from taking the study drug. This survey will take around 15 minutes to complete. During this phone call we will ask them questions about their child's health since starting the study. We will ask them questions about any side effects that your child may have experienced since starting the study drug.
- 2. Phone survey 2:** This phone call will take place between visits 3 and 4 at approximately 18 weeks from the initial study drug start date. This will help us ensure that the study participants does not experience any unwanted side effects from taking the study drug. This survey will take around 15 minutes to complete. During this phone call we will ask them questions about their child's health since starting the study. We will ask them questions about any side effects that your child may have experienced since starting the study drug.

Laboratory evaluations:

We will collect blood samples for safety evaluations as well as for biomarker evaluations.

- Specimens to be collected, amount, schedule:
 - Specimen to be collected: blood, urine
 - Schedule: Blood and urine samples will be collected at screening visit, 7 week visit, 15 week visit, 22 week visit, 30 week visit and 36 week visit
 - Amount: Blood ~ 13 ml (so long as it is not exceeding 2ml/kg body weight limit) each time (~4 ml for liver, thyroid and renal function tests, ~1.5 ml for complete blood counts, ~7.5 ml for biomarker measurement)
Urine ~ 5 ml
- Evaluations to be made:
 - Safety evaluations: They will include liver function tests (SGOT/SGPT, Total bilirubin), renal function tests (serum electrolytes, serum creatinine), thyroid function tests (TSH).
 - Biomarker measurement: Following biomarkers will be evaluated:

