Visit	Informed consent, eligibility criteria (ADOS, Leiter-3)	Adverse event reporting	Medical history, vitals, physical exam	Autism symptom severity (OACIS-S, OACIS-I, ABC, SRS, Vineland Adaptive Behavior Scale)	Blood draw (LFTs, RFTs, TSH, CBC, HSP, mTor, Nerf), urine sample for isoprostanes	Study drug dispensing	Visit duration
Double blind phase (50% participants receive sulforaphane and 50% receive placebo)							
Screening/ baseline visit	X		X	X	X	8 weeks	~ 2.5 hours
3 week phone survey		X					~ 15 minutes

7 week visit		X	X	X	X	7 weeks	~ 1.5 hours
15 week visit		X	X	X	X	8 weeks	~ 1.5 hours
Open label phase (all participants receive sulforaphane)							
18 week phone survey		X					~ 15 minutes
22 week visit		X	X	X	X	7 weeks	~ 1.5 hours
30 week visit		X	X	X	X		~ 1.5 hours
36 week visit		X	X	X	X		~ 45 minutes

11) Data and Specimen Banking*

We plan to store leftover blood and urine samples in -80 C freezer in the Dept. of Pediatrics at UMass and the Cullman Chemoprotection Laboratory at Johns Hopkins for a period of 3 years after completion of the study. They will be accessed by the P.I. or study staff. The samples will continue to be de-identified and labeled with unique study I.D. numbers. The link between the study ID and identifiable information will only be accessible by the UMass personnel. At the end of 3 years the samples will be forever anonymized, and the link between study ID and identifiable information will be destroyed. We will make application to the IRB for any further studies to be conducted, by ourselves or others, using these specimens.

12) Data Management*

Statistical Analysis: The OACIS-I, SRS and ABC data will be analyzed in a mixed model ANOVA with fixed effects for visit, treatment group, and their interaction and random participant-specific intercepts. The effect of sulforaphane on mean change in OACIS-I, SRS and ABC total scores from baseline will be estimated using linear contrasts. Estimates will be unbiased if any loss to follow-up is missing at random, conditional on the observed data and our model assumptions. Significantly greater improvement from baseline in mean scores among participants randomized to sulforaphane based on a two-tailed test at $\alpha = 0.05$ will be taken as support of our primary hypothesis.

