Parents and/or guardians will be responsible for ensuring the timely and complete adherence to daily medication dosage. They will be asked to keep a log of the time of day and the number of capsules taken. They also will monitor for and report any adverse events, undesirable psycho-behavioral reactions throughout the duration of the study or until censorship, should that occur. Parents/guardians will be trained to ensure that the study medication is kept in the original, properly labeled, child-proof containers in a place that is secure from access by siblings, school mates, other children, mentally impaired adults, or pets. Any spilled or lost medication will be documented and reported so that replacement will ensure adherence to prescribed dosages. Parents/guardians will be reminded by telephone at-least 24 hours beforehand of their appointments. Those who miss an appointment will be contacted by telephone in order to elicit the cause and reschedule within one week.

16) **Potential Benefits to Subjects***

Potential benefits of sulforaphane may include demonstrable functional improvements in social responsiveness in subjects with autism. Treatment with sulforaphane may also increase mitochondrial function and decrease oxidative stress, both of which have been subjects of research in autism.

Current treatment standards for children with ASD include various therapy programs, including ongoing speech and language, occupational, physical and behavioral therapies. Many are also in special school programs with Individual Educational Plans. We anticipate that some of the children will be taking prescriptions of antipsychotic, antidepressant, antianxiety or stimulant medications. Approximately 10% will have a history of epilepsy and may be taking anticonvulsants. We will carefully evaluate each medication a subject is taking for potential interactions with sulforaphane. Subjects will continue to participate in their usual therapy programs.

Novelty: This trial of sulforaphane in children with autism provides a novel approach with a strong theoretical basis in clinical observations of the effects of fever in autism. Preliminary evidence from *in vitro* models supports the hypothesized cellular effects of sulforaphane on heat shock proteins Nrf2, mitochondrial functions, and the mTOR pathway.

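### The visit text narrows the side-effect question to serious events at the two double-blind follow-up visits, in conflict with the schedule table and with every other contact

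*Combined protocol and SAP*

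**What the plan says.** All places are in the combined protocol and SAP.

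- Section 10, Study visits narrative, 7 week visit and 15 week visit (double-blind Phase 1), in the same words at each: "They will be asked about any serious side effects they might have experienced".
- Same narrative, 22 week and 30 week visits (open-label Phase 2): "They will be asked about any side effects they might have experienced".
- Same narrative, 36 week visit (off treatment): "Participants and their caregivers will be asked about any side effects they might have experienced".
- Section 10, telephone surveys: the calls are introduced with "In addition there will be two telephone surveys between visit 1 and 2, and between 3 and 4 to detect any possible adverse events". On the first call's timing: "This phone call will take place between visits 1 and 2 at approximately 3 weeks from the study drug start date". The second is at about week 18. Both use the same question: "We will ask them questions about any side effects that your child may have experienced since starting the study drug".
- Section 10, table of procedures by visit: one column, headed "Adverse event reporting", is marked at the week-3 call, weeks 7 and 15, the week-18 call, and weeks 22, 30 and 36.
- Section 13, on risk management: clinical side effects such as flatulence, soft stool and frequent urination are to be monitored, with no limit to one phase.
- Section 15, on the caregivers: "They also will monitor for and report any adverse events, undesirable psycho-behavioral reactions throughout the duration of the study or until censorship". They are also advised to notify staff of the listed side effects.

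**The concern.** Aim 2 (Section 3) asks whether sulforaphane is safe and well tolerated. The side effects that Section 15 expects, such as vomiting, abdominal pain, flatulence, diarrhea and insomnia, are mostly not serious events. Weeks 1 to 15 are the only period in which their frequency on drug can be set against placebo. Yet the two visits that carry the narrower question are exactly the two follow-up visits of that period. Section 15 also says that no study has been designed explicitly to test safety in children, and gives this as the reason for careful evaluation here.

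Two things are at stake: how completely ordinary events are recorded while there is a concurrent placebo group, and whether event counts before and after week 15 mean the same thing.

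**Working it through.** The plan states no figure on this point, so the check is a comparison of the contacts.

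| Contact | Phase | Question in the text | Adverse-event column in table |
|---|---|---|---|
| Week 3 call | 1, double-blind | any side effect | marked |
| Week 7 visit | 1, double-blind | serious only | marked |
| Week 15 visit | 1, double-blind (end) | serious only | marked |
| Week 18 call | 2, open-label | any, since starting study drug | marked |
| Week 22 visit | 2, open-label | any side effect | marked |
| Week 30 visit | 2, open-label | any side effect | marked |
| Week 36 visit | 3, off treatment | any side effect | marked |

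**Prompts for any side effect, by the text.** Phase 1: 1 of 3 contacts. Phase 2: 3 of 3 contacts.

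**Gap in prompting at the time.** From the week-3 call to week 15: 15 − 3 = 12 of the 15 blinded weeks.

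**Later recovery.** The week-18 call asks back to the start of study drug, so it does reach the blinded weeks. An event just after the week-3 call would be recalled over about 18 − 3 = 15 weeks. By then all children are in the open-label phase, and the answer mixes both phases unless onset is dated.

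**Illustration only.** The capture fraction c (the share of Phase 1 events that reach the record by any route) is an assumption; the documents give none. Section 15 reports 12 to 19% on sulforaphane for the listed events in the previous trial, which treated adolescents and adults for 18 weeks (Section 4). With 50 children randomised 1:1 (Section 12), there are 25 on sulforaphane in Phase 1. Expected cases with full capture: 25 × 0.12 = 3.0 and 25 × 0.19 = 4.75. The chance of recording at least one case is 1 − (1 − p × c)^25:

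| Assumed c | p = 12% | p = 19% |
|---|---|---|
| 100% | 95.9% | 99.5% |
| 75% | 90.5% | 97.9% |
| 50% | 78.7% | 91.8% |
| 25% | 53.3% | 70.4% |

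With three to five expected cases per event type, even moderate loss leaves very little to describe. The table shows how the result depends on c; it does not estimate c.

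**Direction.** The question at each Phase 1 contact is the same in both arms, so c is not made to differ by arm through the wording.

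**The case against.** The strongest case against is that this is a drafting slip with no established effect on the data.

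- The narrative does not say that staff ask about nothing else, and nothing gives it precedence over the table, which treats weeks 7, 15, 22 and 30 alike.
- Caregivers must report any adverse event throughout. Both Phase 1 dispensings come with written instructions on recognising side effects and a request to call with concerns.
- The week-18 call looks back over the blinded weeks, and study clinicians are still blind to the Phase 1 assignment.
- Weeks 7 and 15 also include a physical examination, vital signs and the ABC.
- The safety endpoints (Section 9) and the safety analysis (Section 12) are laboratory-based. Section 12 says that the study is not powered to compare safety rates between arms.

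Most of this stands, and it rules out three stronger readings that a reader might infer. First, that ordinary events are under-collected as a fact: other routes exist, so this is a risk that depends on how staff read the text. Second, that the randomised safety comparison is biased: both arms are asked the same thing. Third, that a false rise in events of a known size will appear after the switch to open-label drug: that needs capture rates the documents do not give, must ignore the week-18 look-back, and concerns a phase comparison that the plan does not specify.

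What does not fall away is the conflict. Volunteered reports and recall after the switch do not do the work of a prompt at the visit. The parent log is for dosing times and capsule counts, not symptoms. The word 'serious' also appears in the week-7 and week-15 pause criteria in Section 13, so staff could take it as intended.

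**Conclusion.** The point holds as an internal inconsistency with a limited but real consequence. The text for weeks 7 and 15 is narrower than the schedule table, both calls, the later visits and the Section 13 monitoring statement, and these passages must be reconciled.

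If the narrative is followed literally, the placebo-controlled period risks lower sensitivity for non-serious events, and Phase 1 and Phase 2 rates cannot be compared because they were elicited differently. The effect falls on the descriptive tolerability part of Aim 2 and on what the DSMB sees from the controlled phase. The liver, thyroid and renal toxicity analysis does not depend on the question and is untouched.

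The gap of about 12 weeks and the count of 1 against 3 prompts follow from the text. The number of events lost does not, and no figure should be attached to it beyond an illustration with stated assumptions.

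**What to change.** Delete 'serious' from the side-effect sentence in the 7 week and 15 week visit text. Use one common form with one identical open question (any side effects since the last contact) at every visit from week 7 to week 36 and in both calls. Record onset date, severity and seriousness after the answer, so that each event can be assigned to its phase. This changes data collection only; it does not touch the drug pause or stop criteria.

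The cost is one word deleted in two places, one shared form, and a few more minor events to record at two visits. No visits or calls are added. It should be done before children pass through the blinded visits, because events not asked about then cannot be reliably recovered later.

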Figure 1: Flowchart of progress of study participants through the 3 phases of the clinical trial (flowchart not to scale)

At an initial screening visit, following informed consent by the parents and assent by the child if he or she is able, a complete pre- and postnatal, pediatric and neurodevelopmental history will be obtained. We will also review the child's history of behavioral responses to fever and illness, and rate the parents' recall of subjective impressions of changes in ASD according to the OACIS. Children will be tested using the Autism Diagnostic Observation Schedule (ADOS)²⁹ by a trained clinician. If the diagnosis of ASD is confirmed, nonverbal intelligence will be measured using the Leiter-3³¹.

Monitoring for safety (Specific Aim 2): A complete physical exam will be performed at each of the 6 study visits. Phlebotomies will be performed 6 times, along with urine collection: 1) After screening and prior to randomization; 2) at 7 weeks after starting treatment in Phase 1; 3) at 15 weeks, at the end of Phase 1; 4) at 22 weeks; 5) at 30 weeks, at the end of Phase 2; and 6) at 36 weeks, at the end of the study. Blood samples will be sent for routine laboratory studies at screening, 7, 15, 22 and 30 weeks: complete blood count with differential white blood count; comprehensive metabolic profile, including AST and ALT; thyroid stimulating hormone, in order to monitor for possible adverse effects of sulforaphane in children. Portions of the blood and urine samples will also be processed and stored for research studies as outlined below at screening, 7, 15, 22, 30 and 36 weeks.

Following screening, participating children will be assigned to receive either sulforaphane (2.2 micromoles/kg b.w.) or placebo in Phase 1 by block randomization

using a table of random numbers, by the Research Pharmacy at the UMass Memorial Medical Center. Medication will be supplied to the Research Pharmacy at UMass by the Nutramax Laboratories.

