If the lab results are found to be abnormal (AST/ALT > 2x upper limit of normal, serum creatinine > 1.2 mg/dl, TSH outside normal limits), we will ask the study participants to discontinue study medication for 2 weeks. After 2 weeks, we will ask them to come for an interim study visit and draw their blood for liver function tests, renal function tests and thyroid function tests. If lab values have returned to within study's acceptable limits (AST/ALT < 2x upper limit of normal, serum creatinine < 1.2 mg/dl, TSH within normal limits), and as advised by the study Data Safety Monitoring Board, we will then ask them to resume the study medication.

After 2 weeks, if the lab tests are still abnormal (AST/ALT > 2x upper limit of normal; serum creatinine > 1.2 mg/dl; TSH outside normal limits), then the study participants will discontinue study medication permanently (although we will ask them continue to be followed up in the study).

- 3. 15 week visit (end of double blind Phase 1):** Enrolled subjects will then be asked to come for their 15 week (follow-up) study visit, where OACIS-I, SRS, ABC and Vineland Adaptive Behavior Scale will be administered. A complete physical examination will be performed and vital signs obtained. This visit will take ~ 1.5 hours to complete. They will be asked about any serious side effects they might have experienced. Also, clinical laboratory tests (CBC and platelets, complete metabolic profile (including liver function tests, renal function tests, thyroid function tests), and research laboratory tests blood- (Nrf2, heat shock proteins, measures of oxidative stress and mTOR) and urine sample for isoprostanes will be obtained. Maximum amount of blood drawn at any stage during this study will not exceed 2 ml/kg body weight; we will also not exceed the minimal risk limitation of 3 ml/kg in an 8 week period.

At this visit, we will give the study participants a further 8 week supply of study medication (sulforaphane) that will last until the next (22 week) visit plus a one-week buffer. We will provide detailed instructions for subjects/parents/guardians on how to take the study medication along with the medication package, and they will be made aware (and given written instructions) on how to recognize any side effects associated with the study medication. They will be asked to call the study staff in case they have any questions or concerns.

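### Minor, cheap improvement: Phase 1 drug runs out on the nominal day of the week-15 visit, leaving no reserve if that visit is rescheduled within a week

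*Combined protocol and SAP*

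**What the plan says.** All references are to the combined protocol and SAP.

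- **Length of treatment** (section 10, Study visits narrative): "The main study will consist of 2 phases of treatment, each lasting 15 weeks per patient". Dosing is once daily (section 10, Dosage and administration).
- **First pack** (screening/baseline visit): "we will mail the study participants (or ask their parents to pick up) an 8 week supply of study medication", described as stock "that will last until the 7 week visit, plus a one week buffer".
- **Second pack** (7 week visit): "a further 7 week supply of study medication (sulforaphane or placebo) that will last until the next visit (15 week visit"). On the order of use: "Study participants will be asked to finish the medication from the previous lot before starting the latter batch".
- **Third pack** (15 week visit, open label): "a further 8 week supply of study medication (sulforaphane) that will last until the next (22 week) visit plus a one-week buffer". The procedures table at the end of section 10 repeats the 8, 7, 8, 7 pattern.
- **Visit clock** (section 10, Monitoring for safety): blood is drawn "2) at 7 weeks after starting treatment in Phase 1; 3) at 15 weeks, at the end of Phase 1".
- **Late visits** (section 15): "Those who miss an appointment will be contacted by telephone in order to elicit the cause and reschedule within one week". The same paragraph provides a reminder call at least 24 hours ahead, a dosing log kept by parents, and replacement of spilled or lost drug. It does not mention drug to cover a postponed visit.
- **Return of unused drug**: the pilot asks for it at its second visit (section 10). The main trial asks for it only after a seizure or an unresolved behaviour change (section 13).

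**The concern.** The one-week buffer in the first pack is used up in week 8, because that pack is finished before the second is opened. Nothing is then left over at week 15, although weeks 7 and 22 each have a stated spare week. A family that follows the dosing instructions and the rescheduling rule can therefore arrive with no drug for several days.

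Week 15 closes the only randomized, blinded comparison. The OACIS-I difference is powered there, the ABC and SRS responder cut-offs are set there (section 12), and safety and research blood is drawn at the same visit. A placebo child loses nothing by running out. A sulforaphane child might lose some benefit, which would pull the arms together.

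**Working it through.** **Inputs.** Phase 1 is 15 weeks, once daily, so 15 x 7 = 105 doses are needed. The packs hold 8 x 7 = 56 and 7 x 7 = 49 doses. Visits are counted from the start of treatment.

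**Step 1: the plan's own supply.** 56 + 49 = 105 doses, which reproduces the stated 15 weeks exactly.

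**Step 2: reserve at each visit** (doses supplied in the phase minus doses needed).

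| Visit | Supplied | Needed | Reserve (days) |
|---|---|---|---|
| Week 7 | 56 | 49 | 7 |
| Week 15 | 105 | 105 | 0 |
| Week 22 | 56 | 49 | 7 |
| Week 30 | 105 | 105 | 0 |

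**Step 3: days off drug at a late week-15 visit.** Let S be doses supplied, d days late, and a the fraction of days dosed, spread evenly (an assumption). Supply lasts S/a days, so days off drug = max(0, 105 + d - S/a). The gap disappears at a = S/(105 + d) or lower.

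| S | d | a = 1.00 | a = 0.98 | a = 0.95 | No gap at or below |
|---|---|---|---|---|---|
| 105 | 3 | 3.0 | 0.9 | 0 | 97.2% |
| 105 | 7 | 7.0 | 4.9 | 1.5 | 93.75% |
| 112 | 3 or 7 | 0 | 0 | 0 | any level |

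For example, at d = 7 and a = 0.95: 112 - 105/0.95 = 112 - 110.5 = 1.5 days. A child who had a 14-day pause and otherwise took every dose has used 91 doses, so 105 - 91 = 14 remain and there is no gap.

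**Step 4: upper bound on the effect.** With 50 children randomized 1:1, the sulforaphane arm has 25. If one child lost the full planned difference of 4 units, the arm mean would move by 4/25 = 0.16 units, or 0.16/4.9 = 0.03 of the assumed standard deviation.

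**Step 5: leftover Phase 1 doses at an on-time week-15 visit** (S - 105a).

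| S | a = 1.00 | a = 0.95 | a = 0.90 |
|---|---|---|---|
| 105 (current) | 0 | 5.25 | 10.5 |
| 112 (extra week) | 7 | 12.25 | 17.5 |

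**The case against.** **The plan supplies what it promises, in a regular pattern.** Fifteen weeks of drug are given for fifteen weeks of treatment. A reader who sets the 7-week pack against the 8-week gap from week 7 to week 15 might infer a missing week. The documents do not support that, because the spare week from the first pack fills it. Week 30 also has zero reserve, so the buffer falls at mid-phase visits and not at phase ends, where the product changes or stops. The protocol does not give this as a reason, but the pattern argues against oversight. This stands, and is why the point is an improvement and not an error. Week 30 matters less because it is not a randomized comparison.

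**The clock may leave hidden reserve.** The narrative counts six visits over 36 weeks, with screening as the first. If week 15 ran from screening, the wait for laboratory results and delivery would leave a few spare days (a lag of 3 days gives 3, a lag of 7 gives 7; both lags are assumed). But the safety-monitoring text counts week 7 from the start of treatment, and the phone surveys are also timed from the drug start date. The zero-reserve reading is better supported.

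**The harm needs two things together.** The visit must be late and adherence nearly complete. The documents give no rate for either. The reminder and missed-visit calls make long delays less likely. This stands.

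**An extra week for everyone creates leftovers.** Half the children would hold surplus placebo when open-label drug begins, having been told at week 7 to finish the old lot first. Late children could also exceed 15 weeks of blinded treatment. This stands as a real cost. It makes tablet return essential under that option and favours bridging only the late children.

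**Conclusion.** The point holds as a minor, inexpensive improvement. Under the plan's own rules, a near-fully adherent sulforaphane child can be assessed at week 15 after up to 7 days off drug, and no text provides drug for that interval. This rests on visits being timed from the start of treatment, on a visit held up to 7 days late, and on missed doses being spread evenly.

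Three stronger readings are tempting and should not be drawn.

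- **That the primary comparison is materially weakened.** The 0.16-unit bound per affected child requires the entire benefit to vanish within days. The protocol gives no behavioural or biomarker offset time, so the true amount is unknown and probably well below the bound.
- **That the gap could favour sulforaphane.** Running out can only shrink a true difference between arms, so it adds no false-positive risk for efficacy.
- **That children could be two weeks off drug.** This needs the rescheduling sentence to mean only that a new date is agreed within a week. That is a strained reading.

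**What to change.** 1. **Cover a week-15 visit up to 7 days late**, by one of two routes:
   - dispense 8 weeks instead of 7 at the week-7 visit, changing the narrative and the procedures table, for 56 + 56 = 112 doses; or
   - in section 15, offer blinded bridging drug by mail or pick-up on the call made to a family that misses the visit, from day 105 onward. Both delivery routes are already used for the first pack. This reaches only late children and leaves fewer spare tablets, but mailing time may leave a short gap.
2. **Under either route, collect and count all unused Phase 1 tablets at week 15 before open-label drug is handed out.** This keeps placebo out of Phase 2. It is worth doing under the current supply too, since 5.25 doses remain at 95% adherence and 14 after a two-week pause.
3. **Record days off drug at the week-15 visit** from the parent log.

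**Cost.** An extra week for all takes 3 x 7 = 21 to 8 x 7 = 56 tablets per child. For 50 children that is between 1,050 and 2,800 tablets, plus packing. An on-time, fully adherent child would hold 7 leftover Phase 1 doses instead of 0. Bridging needs drug only for late children, plus handling by the research pharmacy to keep the blind. Both routes need a short text change and tablet accountability at an existing visit. The daily dose, planned visit schedule and analysis do not change.
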